### 8.2.1 Hospitalization – Prolongation of existing hospitalization

Hospitalization is defined as an overnight stay in a hospital unit and/or emergency room.

An additional overnight stay defines a prolongation of existing hospitalization.

The following is not considered an SAE/SADE and should be reported as an AE/ADE only:

- Treatment on an emergency or out subject basis for an event not fulfilling the definition of seriousness given above and not resulting in hospitalization.

The following reasons for hospitalizations are not considered AEs, and therefore not SAEs:

- Hospitalizations for cosmetic elective surgery, social and/or convenience reasons.
- Standard monitoring of a pre-existing disease or medical condition that did not worsen, e.g., hospitalization for coronary angiography in a subject with stable angina pectoris.
- Elective treatment of a pre-existing disease or medical condition that did not worsen, e.g., hospitalization for chemotherapy for cancer, elective hip replacement for arthritis.

### 8.2.2 SAEs /sADE related to study-mandated procedures

Such SAEs /SADEs are defined as SAEs/SADEs that appear to have a reasonable possibility of causal relationship (i.e., a relationship cannot be ruled out) to study-mandated procedures (excluding administration of medical device) such as discontinuation of subject's previous treatment or complication of a mandated invasive procedure (e.g., blood sampling, heart catheterization), or car accident on the way to the hospital for a study visit, etc.

### 8.2.3 Pregnancy

Any pregnancy that occurs during study participation must be reported to the principal investigator/sponsor. **To ensure subject safety, each pregnancy must be reported to the principal investigator/sponsor immediately.** A pregnancy must be followed up to determine outcome

(including premature termination) and status of mother and child. Pregnancy complications and elective terminations for medical reasons must be reported as an AE/ADE or SAE. Spontaneous abortions must be reported as an SAE.

Any SAE occurring in association with a pregnancy, brought to the investigator's attention after the subject has completed the study and considered by the investigator as possibly related to the investigational product, must be promptly reported to the principal investigator/sponsor.

In addition, the investigator must attempt to collect pregnancy information on any female partners of male study subjects who become pregnant while the subject is enrolled in the study. Pregnancy information must be reported to the principal investigator/sponsor as described above.

*Please enter the address of Investigator/Sponsor!*

### 8.3 Severity of adverse events/adverse device effects

The severity of clinical AEs /ADEs is graded on a three-point scale: mild, moderate, severe, and reported on specific AE pages of the CRF.

If the severity of an AE/ADE worsens during medical device administration, only the worst intensity should be reported on the AE page. If the AE lessens in intensity, no change in the severity is required.

#### **Mild**

Event may be noticeable to subject; does not influence daily activities; the AE /ADE resolves spontaneously or may require minimal therapeutic intervention;

#### **Moderate**

Event may make subject uncomfortable; performance of daily activities may be influenced; intervention may be needed; the AE/ADE produces no sequelae.

#### **Severe**

Event may cause noticeable discomfort; usually interferes with daily activities; subject may not be able to continue in the study; the AE/ADE produces sequelae, which require prolonged therapeutic intervention.

A mild, moderate or severe AE/ADE may or may not be serious. These terms are used to describe the intensity of a specific event (as in mild, moderate, or severe myocardial infarction). However, a severe event may be of relatively minor medical significance (such as severe headache) and is not necessarily serious. For example, nausea lasting several hours may be rated as severe, but may not be clinically serious. Fever of 39°C that is not considered severe may become serious if it prolongs hospital discharge by a day. Seriousness rather than severity serves as a guide for defining regulatory reporting obligations.

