**7.5 Benefit and risk assessment**

A recent safety study summarizes the adverse events of acupuncture. Wheway J et al analyzed 325 incidents during acupuncture treatment. Adverse events reported include retained needles (31%), dizziness (30%), loss of consciousness/unresponsive (19%), falls (4%), Bruising or soreness at needle site (2%), Pneumothorax (1%) and other adverse reactions (12%). The majority (95%) of the incidents were categorised as low or no harm [Wheway J et al, 2012]. On auricular acupuncture in particular we found no safety data. We expect a similar safety profile to body acupuncture.

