### 8.5 Reporting procedures

A special section is designated to adverse events/ADEs in the case report form. The following details must thereby be entered:

- Type of adverse event/ADE
- Start (date and time)
- End (date and time)
- Severity (mild, moderate, severe)
- Serious (no / yes)
- Unexpected (no / yes)
- Outcome (resolved, ongoing, ongoing – improved, ongoing – worsening)
- Relation to medical device (unrelated, possibly related, definitely related)

Device related adverse events are to be documented in the case report form in accordance with the above mentioned criteria and reported to the Sponsor.

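### Section 8.3 separates Moderate from Severe by sequelae, against its own intensity rule and examples, and the outcome list in 8.5 has no code for death or resolution with sequelae

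*Combined protocol and SAP*

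**What the plan says.** Section 8.3 sets the scale: "The severity of clinical AEs /ADEs is graded on a three-point scale: mild, moderate, severe". If an event worsens while the device is in use, only its worst intensity is reported.

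The three definitions include:

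- Mild: "does not influence daily activities; the AE /ADE resolves spontaneously or may require minimal therapeutic intervention".
- Moderate: some discomfort and a possible effect on daily activities, then "intervention may be needed; the AE/ADE produces no sequelae".
- Severe: possible marked discomfort, everyday life disturbed as a rule, and perhaps an early end to participation. To these the definition adds, without any qualifier, that "the AE/ADE produces sequelae, which require prolonged therapeutic intervention".

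The paragraph that closes the Severe entry says the terms express how intense an event is. It mentions a severe headache as something of minor medical importance and adds that "nausea lasting several hours may be rated as severe, but may not be clinically serious". It also says that regulatory reporting follows seriousness, not severity.

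Section 8.5 lists what must be entered on the CRF for each event. The outcome field reads "Outcome (resolved, ongoing, ongoing – improved, ongoing – worsening", and nothing follows in that list. Section 8.2 makes death and permanent impairment criteria for an SAE. Section 8.5.1 requires an initial SAE report and a follow-up report, and the outcome is to be described.

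**The concern.** A severity grade is useful only if two investigators looking at the same event would choose the same grade. Here the definition points to one grade and the explanatory text to another, and the disagreement falls on events that are intense but leave nothing behind. The CRF also never records as an outcome the sequelae on which the Severe grade partly depends.

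Recording adverse events is a stated secondary objective, and section 7.5 says no safety data were found for auricular acupuncture in particular. A usable description of severity and outcome is therefore part of what this pilot should deliver. With 20 patients per group, a few events graded one way or the other would visibly change any summary by severity.

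**Working it through.** The plan gives no figure on this point, so the check sets its provisions side by side.

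**Step 1: what separates the grades (section 8.3).**

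| Element | Mild | Moderate | Severe |
|---|---|---|---|
| Daily activities | not affected | possibly affected (hedged) | usually affected (hedged) |
| Staying in the study | not mentioned | not mentioned | possibly not (hedged) |
| Sequelae | not mentioned | none (unhedged) | present and needing prolonged treatment (unhedged) |

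Between Moderate and Severe, the sequelae clause is the only element stated without a qualifier. It is the only firm dividing line.

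**Step 2: apply the scale to two kinds of event.**

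- *Intense, disabling for some hours, then fully resolved.* Read literally, it fails the sequelae clause of Severe and satisfies that of Moderate, so it is Moderate. By the intensity statement and the nausea example, it may be Severe. The two readings cannot both be followed.
- *Leaves sequelae that need no prolonged treatment.* It fails Moderate, which allows no sequelae. It also fails Severe, which requires sequelae needing prolonged intervention. It fits neither grade.

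**Step 3: compare the outcome codes (section 8.5) with the outcomes that can occur.**

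| Outcome | Codes that fit, of 4 | Other place in the plan |
|---|---|---|
| Death | 0 | SAE criterion (8.2); narrative in the SAE reports (8.5.1) |
| Resolved with sequelae, serious (e.g. permanent impairment) | 0 | as above |
| Resolved with sequelae, not serious | 0 | none defined |

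In the first two rows the information exists, but only as free text outside the coded field. In the third row the nearest code is plain resolved or ongoing, and neither says that a deficit remains.

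**The case against.** The strongest reply has four parts.

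*No rule says every element of a grade must be met.* The definitions are lists of mostly hedged descriptors, and an investigator who reads all of 8.3 is told that a transient event may be severe. This stands. It makes under-grading conditional on a literal reading; the secure claim is inconsistent grading. It does not remove the contradiction, because the plan does not say which part prevails.

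*The worst outcomes are captured elsewhere.* A reader might infer from 8.5 that deaths and lasting harm go unrecorded. The documents do not support that: 8.2 makes them SAEs, the adverse event page has a yes/no field for serious, and 8.5.1 asks for the outcome in the reports. What is missing is the code.

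*Nothing shows that the device is favoured.* A reader might infer that the scale makes the device look milder than it is. One scale serves both arms, and patient and investigator are blinded, so the wording shows no mechanism that would bias the device-placebo comparison. Section 10.6 also specifies no analysis by severity. Both points stand, although severity remains a mandatory entry on the CRF.

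*The incident figures in 7.5 do not size the problem.* A reader might add dizziness (30%) and loss of consciousness (19%) to get 49% of 325 incidents, about 159, and treat them as events barred from Severe. Those are shares of reported acupuncture incidents, not expected rates in this trial. The section does not say how many were incapacitating or left sequelae. It classes 95% as low or no harm, which leaves 0.05 × 325, about 16. Harm category is not intensity, so that figure does not size the problem either.

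One further objection concerns the remedy. Deleting the sequelae clauses alone would remove the only unhedged separator and leave a vaguer boundary. This is right, and the fix has to replace the boundary as well.

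**Conclusion.** The point holds as an internal contradiction in the grading rule, a gap between two grades, and an incomplete outcome list. It is a minor to moderate matter of safety data quality that should be corrected, preferably before enrolment, because regrading events afterwards is unreliable.

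The number of events affected cannot be estimated from the documents. The definite count is that none of the four outcome codes covers death or resolution with sequelae.

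The conclusion assumes that the CRF page carries the outcome list as printed in 8.5, and that no separate grading instruction settles which part of 8.3 prevails. Neither the CRF nor such an instruction is among the documents.

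**What to change.** In 8.3, delete the sequelae clauses from Moderate and Severe so that the grade rests on intensity and interference with daily activities. In the same edit, replace the hedged wording on daily activities with a firm boundary, for example Moderate: daily activities limited; Severe: daily activities prevented.

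In 8.5, extend the outcome list to: resolved, resolved with sequelae, ongoing, ongoing-improved, ongoing-worsening, fatal. This lets lasting harm be tabulated under outcome, whether or not the event was serious, and brings the codes into line with the SAE criteria in 8.2.

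The cost is a few changed phrases and two more tick boxes on the adverse event page. The count of severe events may rise, because intense reversible events would then be graded by their intensity.

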### 8.4 Relationship to medical device

For alls, the investigator will assess the causal relationship between the medical device and the AE/ADE using his/her clinical expertise and judgment according to the following algorithm that best fits the circumstances of the AE/ADE:

#### **Unrelated**

- May or may not follow a reasonable temporal sequence from administration of the study product

- Is biologically implausible and does not follow known response pattern to the suspect medical device (if response pattern is previously known)
- Can be explained by the known characteristics of the subject's clinical state or other modes of therapy administered to the subject.

#### Possible related

- Follows a reasonable temporal sequence from administration of the medical device.
- May follow a known response pattern to the medical device (if response pattern is previously known).
- Could not be reasonably explained by the known characteristics of the subject's clinical state or other modes of therapy administered to the subject, if applicable.

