#### Definitely related

- Follows a reasonable temporal sequence from administration of the medical device.
- Follows a known response pattern to the medical device (if response pattern is previously known).
- No other reasonable cause is present.

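### The Possible related grade shuts out events that heart failure or its therapy could also explain, so a well-timed, device-plausible event with competing causes fully meets none of the three causality grades

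*Combined protocol and SAP*

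**What the plan says.** Section 8.4 (Relationship to medical device) asks the investigator to use clinical judgment "according to the following algorithm that best fits the circumstances of the AE/ADE". Three grades follow, each with three bullets.

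- **Unrelated**: timing may or may not fit; the event "Is biologically implausible and does not follow known response pattern to the suspect medical device"; and it "Can be explained by the known characteristics of the subject's clinical state or other modes of therapy administered to the subject".
- **Possible related**: timing fits; the event may follow a known response pattern; and it "Could not be reasonably explained by the known characteristics of the subject's clinical state" or by other therapy, if applicable.
- **Definitely related**: timing fits; the event follows a known response pattern; and "No other reasonable cause is present".

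The pattern bullets apply only if a response pattern is already known. Section 8.4 does not say whether all bullets of a grade must be met, or what to do when none or several grades fit.

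Section 8.5 (Reporting procedures) offers only these three grades on the CRF. It requires device-related events to be documented "in accordance with the above mentioned criteria and reported to the Sponsor".

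**The concern.** A middle causality grade normally holds events for which the device is a credible cause but not the only one. Here its third bullet removes them, because any reasonable explanation from the underlying disease or its treatment disqualifies the event.

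Such events are foreseeable. All 40 planned patients have chronic heart failure (section 6.1.1), and section 8.1.1 counts worsening of a pre-existing disease as an adverse event. By its nature the clinical state can explain such worsening. That the device could also be a plausible cause of some of these events is an inference from its intended autonomic action, not something the plan states.

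At stake is the consistency of attribution. Adverse events of the stimulation are a secondary objective (synopsis and 5.2 Secondary Objectives), and section 7.5 reports that no safety data specific to auricular acupuncture were found. Two investigators could grade the same event differently, and the wording leans towards the grade that clears the device.

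**Working it through.** The plan gives no figure to reproduce. The check sets the bullets of section 8.4 against each kind of event.

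**Inputs.** Take events with a reasonable temporal sequence, so that every timing bullet is met. Let P = 1 if the event is plausible for the device and follows a known response pattern, and 0 if neither holds. Let E = 1 if the clinical state or other therapy reasonably explains it, and 0 if not.

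**Rules.** A grade is fully met when all its bullets are met:

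- Unrelated: P = 0 and E = 1.
- Possible related: E = 0 (its pattern bullet is permissive, so always met).
- Definitely related: P = 1 and E = 0.

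| P | E | Grades fully met, current text |
|---|---|---|
| 1 | 1 | none |
| 1 | 0 | Possible, Definitely |
| 0 | 1 | Unrelated |
| 0 | 0 | Possible |

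One of the four well-timed combinations has no fully matching grade. It fails Unrelated because it is not implausible, Possible related because it can be explained otherwise, and Definitely related because another reasonable cause is present.

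**Does the result depend on a known response pattern?** No. Suppose the event is plausible but no pattern is known, so the pattern bullets lapse. It still fails Unrelated on plausibility, and it still fails the third bullet of each of the other two grades. Other rows may change, but this one stays empty.

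**Does it depend on requiring all bullets?** If one bullet were enough, the event would meet all three grades at once, since each has at least one bullet it satisfies. That does not assign a grade either.

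**Direction.** Unrelated is the only grade whose text describes an event with another explanation. An assessor guided by that feature would choose it.

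**After the change proposed below.** Possible related is then met if E = 0, or if E = 1 and a relationship is plausible and cannot be ruled out.

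| P | E | Grade assigned |
|---|---|---|
| 1 | 1 | Possible |
| 1 | 0 | Definitely (higher of two fully met) |
| 0 | 1 | Unrelated |
| 0 | 0 | Possible |

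Well-timed combinations without a grade fall from one of four to none.

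**The case against.** The strongest reply is that section 8.4 relies on judgment and best fit, not on a checklist. The plan never says that all bullets must be met, so an investigator can always choose a grade. This stands as far as it goes: the event can be graded. But best fit gives no rule for choosing when the device and the disease are both credible causes, and the third bullet of Possible related still argues against the natural choice.

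The second reply is that little hangs on the grade, and most of this stands. Serious events are reported to the ethics committee and the authority whatever their relatedness (sections 8.5.1 and 12.2). The sponsor reviews the assessment of all adverse events and documents their relationship in writing (8.5.1). Early termination (6.1.6) is not tied to the grade, and no summary by causality is planned. Sponsor review is a safeguard, but section 8.5.1 supplies no other criteria for relatedness.

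Third, the check covers well-timed events only. Of the four combinations without reasonable timing, three also fully meet no grade. That is a separate looseness in the wording, which this change does not address.

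Stronger readings are tempting but not supported:

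- A reader might infer that Possible related covers no uncertain causality, since every event meeting Definitely related also meets it. The P = 0, E = 0 row shows otherwise: it covers unexplained events that follow no known pattern. What it omits is competing causes.
- A reader might count bullets and conclude that the three grades tie exactly. The plan prescribes no counting or equal weights, and the tie appears only if a response pattern is taken as known.

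**Conclusion.** The point holds, and it is minor. As written, the third bullet of Possible related excludes a well-timed, device-plausible event that heart failure or its therapy could also explain, and neither of the other grades fits it in full. Under-attribution is possible, but its size cannot be shown.

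The consequence is confined to the relatedness entry in the CRF and to the section 8.5 reporting of device-related, mainly non-serious, events to the sponsor. A reader might infer that serious events could go unreported; sections 8.5.1 and 12.2 do not support that.

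Nor can the number of affected events be computed. Section 7.5 says "We expect a similar safety profile to body acupuncture" and lists types of incident, which a reader might use to size the problem. Those are shares of incident reports from body acupuncture. They are not rates per patient, and they do not show which events would have competing causes.

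The conclusion assumes that the bullets of a grade are meant to be read together, which is natural but unstated, and that some events in this population will have both a plausible device cause and a plausible disease or therapy cause.

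**What to change.** Replace the third bullet of Possible related with: *Either the subject's clinical state or other therapy does not reasonably account for the event, or it does, but a relationship to the device is also plausible and cannot be ruled out.* The protocol already uses the idea that a relationship cannot be ruled out in section 8.2.2, for serious events from study procedures.

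Keep "No other reasonable cause is present" as what separates Definitely related. Add to the opening of section 8.4 that the higher grade applies when two grades are fully met. Align the CRF guidance.

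The cost is one bullet, one sentence and the matching guidance. Some more events will be graded possibly related, by a number that the documents do not allow to be estimated. Events that are implausible for the device and otherwise explained stay Unrelated.

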#### Definitely related

- Follows a reasonable temporal sequence from administration of the medical device.
- Follows a known response pattern to the medical device (if response pattern is previously known).
- No other reasonable cause is present.

### 8.5 Reporting procedures

A special section is designated to adverse events/ADEs in the case report form. The following details must thereby be entered:

- Type of adverse event/ADE
- Start (date and time)
- End (date and time)
- Severity (mild, moderate, severe)
- Serious (no / yes)
- Unexpected (no / yes)
- Outcome (resolved, ongoing, ongoing – improved, ongoing – worsening)
- Relation to medical device (unrelated, possibly related, definitely related)

Device related adverse events are to be documented in the case report form in accordance with the above mentioned criteria and reported to the Sponsor.

#### 8.5.1 Reporting procedures for SAEs/SADEs

In the event of serious, the investigator has to use all supportive measures for best patient treatment. A written report is also to be prepared and made available to the clinical investigator immediately. The following details should be at least available:

- Patient initials and number
- Patient: date of birth, sex, ethical origin
- The suspected medical device
- The adverse event assessed as serious
- Short description of the event and outcome
- Device related or non-device related

The written report is divided into two parts:

- Initial report: Informs about what has happened (AE/ADE assessed as serious), if there is a relationship to the medical device ... and which action was set.
- Follow up-Report: informs about the outcome

The Sponsor is responsible for the classification of adverse events and ongoing safety evaluation of the clinical investigation and shall:

- review the investigators assessment of all adverse events and determine and document in writing their seriousness and relationship to the investigational device; in case of disagreement between the sponsor and principal investigator(s)
- review all devices deficiencies and determine and document in writing whether they could have led to a serious adverse device effect; in case of disagreement between the sponsor and the principal investigator(s)
- report or ensure the reporting , to the EC and regulatory authorities (AGES) of all serious adverse events and devices.

